### **3. Study Design**

This randomized controlled trial builds on a pilot trial of the Siempre Seguiré intervention. We will conduct 4 intervention groups and 4 wait-list control groups of 15 participants each (n=120). After participants complete the baseline assessment, we will randomize them into the intervention and wait-list control groups. We will provide the program to any interested control participants shortly after the 6-month follow-up surveys are completed. Our proposed sample size (60/condition) is consistent with those recommended for small intervention tests in staged intervention development.

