### **4. Methods**

#### *Screening/Recruitment*

As in our prior pilot test, we will recruit participants via fliers left at the clinic at which the intervention will be conducted (Bienestar) and other AIDS service organizations (ASOs) (in waiting areas, on bulletin boards), fliers disseminated by Bienestar staff (e.g., case managers) to clients, and online advertisements. We will hold brief information sessions at client and staff gatherings. We will hire a

research assistant from the local community for recruitment and tracking who is well-connected with the local HIV population and familiar with local HIV services for Latinos.

Participants will be eligible if they are  $\geq 18$  years-old, are HIV-positive (verified by medication bottles or copies of laboratory results), were biologically male at birth and identify as male, identify as Latino, and report having sex with men in the past 12 months. To maximize chances of showing effects, participants must also either be not on antiretroviral treatment (ART) OR not fully engaged in care (i.e., less than 2 visits in the past 12 months) and/or missed at least 1 ART dose in the past month. Transgender women will not be included because they face discrimination regarding gender identity, which would necessitate a differently tailored intervention.

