To validate self-reports, we will obtain HIPAA consent for appointment attendance in the last year from **medical records**, from which we will examine whether the participant had at least one HIV medical care visit in each 6-month period over the last 12 months, with a minimum of 60 days between visits. Participants will list all prescribed ART medications using medication bottles (brought to the interview). Adherence will be measured continuously and electronically from baseline to 6-month follow-up with the **Medication Event Monitoring System (MEMS)**. At baseline (~2 months prior to the first intervention session, to allow time for any reactance to the MEMS assessment to decrease prior to the intervention), interviewers will assist clients with dispensing the medication with the most complex dosing schedule or the base medication of the regimen if all medications have the same schedule (e.g., non-nucleoside reverse transcriptase inhibitor, protease inhibitor, integrase inhibitor), into a MEMS bottle. Monthly from 2-6-months post-baseline, interviewers will download adherence data and participants will report instances in which the cap was not used as intended in the past 2 weeks (how often the bottle was opened without removing a dose, a dose was taken from a source other than the bottle, such as a pillbox, and whether multiple doses were removed at a time and "pocketed" for later ingestion). Data for the past two weeks at each time-point will be adjusted using these responses for a more valid assessment. MEMS software calculates the percentage of total scheduled doses actually taken, which will be dichotomized at  $\geq 85\%$  of doses taken at each time-point, following research suggesting that moderate adherence has clinically significant effects. We will assess self-reported adherence using items validated against viral load and pill counts: number of doses missed last week; percentage of prescribed medications taken last month (on a visual analogue scale), and ability to take all medications as prescribed in the past 4 weeks. We will obtain HIPAA consent to extract the last two viral load values from medical records. Viral load suppression will be defined as  $< 200$  copies of virus per milliliter of blood plasma.

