## 5. Statistical Analysis

Consistent with R34 guidelines, our primary purposes are to develop the intervention and collect preliminary data regarding feasibility and acceptability; conducting formal statistical tests of outcomes or attempting to obtain a measure of effect size is not justified with a limited sample size. Thus, the proposed analyses are meant to be exploratory, to aid in planning for a full RCT. We do not expect to have sufficient statistical power to adequately examine program effects in multivariate models. However, we will explore bivariate effects in the proposed analyses, and will also examine use of a small set of covariates.

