We will explore whether the program improves coping responses to discrimination; reduces medical mistrust, distress, and internalized stigma; improves adherence and retention in care; and increases rates of viral suppression in the intervention vs. control group. We will use generalized linear mixed models, i.e., a repeated-measures linear regression approach to predict coping with data collected at baseline and 4- and 6-month follow-up that compares differences between intervention and control means over time. We will employ a parallel repeated-measures logistic regression approach to predict optimal adherence (i.e., dichotomous adherence,  $\geq 85\%$  of doses taken) with electronic monitoring data collected at baseline and 2, 4, and 6-month follow-up. We will conduct logistic regressions predicting viral load (dichotomized as suppressed vs. not suppressed) at 6-months post-baseline with dichotomized baseline viral load. We will use similar repeated-measures linear models to examine intervention effects on the other secondary outcomes, as well as on linear adherence (percentage of prescribed doses taken) and log viral load change from baseline. We will select covariates from variables that are hypothesized on the basis of theory and previous research to predict outcome variables (see Fig. 1), and for which we find support for hypotheses in bivariate baseline analyses. We will use intention-to-treat analysis, i.e., we will analyze participants according to the condition to which they were randomized, regardless of their subsequent session attendance. We will account for all participants who responded to the baseline survey, regardless of follow-up survey or item completion, using nonresponse weighting or multiple imputation, as appropriate. Because each participant will complete the baseline survey prior to randomization, we will compare follow-up survey respondents with nonrespondents on demographics and medical variables. If we have high survey participation and find significant differences between respondents and nonrespondents, we will use inverse predicted probability nonresponse weights (and use linearization to correct estimated standard errors if there are modest deviations from standard statistical inference assumptions). We will address item nonresponse through multiple imputation.

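### The 6-month suppression model uses baseline viral load only as suppressed or not; adding the recorded value among unsuppressed men would bring a small, conditional efficiency gain

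*Combined protocol and SAP*

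**What the plan says.** The combined protocol and SAP, section 5 (Statistical Analysis), specifies logistic regressions "predicting viral load (dichotomized as suppressed vs. not suppressed) at 6-months post-baseline with dichotomized baseline viral load". The cut comes from section 4, under Procedures: "Viral load suppression will be defined as" fewer than 200 copies per millilitre of plasma.

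The number behind the category will be in the data set. Procedures states: "We will obtain HIPAA consent to extract the last two viral load values from medical records". Section 5 also extends the linear repeated-measures models to further outcomes, "as well as on linear adherence (percentage of prescribed doses taken) and log viral load change from baseline", which cannot be computed without a numeric baseline.

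Section 5 allows other adjustment in general terms (the team "will also examine use of a small set of covariates") but does not name numeric viral load for the suppression model. It also sets the status of all outcome analyses: "conducting formal statistical tests of outcomes or attempting to obtain a measure of effect size is not justified with a limited sample size".

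**The concern.** Eligibility (section 4, Screening/Recruitment) admits men who are "not on antiretroviral treatment (ART) OR not fully engaged in care", and also men on treatment who missed as little as one dose in the past month. Baseline loads among unsuppressed men could therefore span several log10 units. If men further above 200 copies/mL are less likely to be suppressed at 6 months, the numeric value predicts the outcome within the one group that can newly gain suppression. The planned covariate is constant in that group.

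What is at stake is efficiency. With about 60 men per arm, chance differences between arms in how far unsuppressed men lie above the cut remain as unexplained variation, and information already collected could remove some of it.

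**Working it through.** **The plan's own figure.** (4 + 4) groups × 15 = 120 men, 60 per condition, which agrees with section 3. The documents give no alpha, power, effect size or suppression rate for this model, so there is no power statement to reproduce.

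**The coding.** With the cut at 200, 250 and 250,000 copies/mL both count as unsuppressed. They differ by log10(250,000/250) = 3.

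**The models.** Let T be arm, V baseline viral load, and U = 1 if V ≥ 200 and 0 otherwise.

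- Planned: logit P(suppressed at 6 months) = a + b·T + c·U
- Extended: logit P = a + b·T + c·U + d·U·log10(V)
- Standardized risk difference: the mean over all men of [fitted P with T = 1 − fitted P with T = 0]

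**Assumptions, none from the documents.** 120 men, 1:1 allocation, exact baseline values, no dropout, no clustering by group. The slope is the fall in log-odds of suppression per log10 among unsuppressed men.

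**Check 1: test efficiency** (ratio of squared mean z for arm, extended to planned; true odds ratio 2.5, ln 2.5 = 0.916). With 30–50% suppressed at baseline and unsuppressed values spread over 2.3–5.3 log10, 1,500 trials per setting gave ratios of 1.01–1.02, 1.04–1.06 and 1.12–1.15 at slopes 0.5, 0.8 and 1.2. Widening to 30–70% suppressed gave:

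| Slope | Change in test efficiency |
|---|---|
| 0 | about 1% loss |
| 0.5 | 0–2% gain |
| 0.8 | 2–8% gain |
| 1.2 | 7–16% gain |

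The largest power gain was about 6 percentage points, and type I error stayed near 5%. In men, 1% of 120 is 1.2 and 15% is 18.

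**Check 2: risk difference** (3,000 trials per setting; log odds ratio 0.9; 40%, 60% and 75% suppressed; unsuppressed values log-uniform from 200 to about 316,000 copies/mL). Three entries in a cell are for 40%, 60% and 75% suppressed.

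| Slope | Variance, planned ÷ extended | Power, planned → extended |
|---|---|---|
| 0 | 0.99, 0.99, 0.99 | 0.576→0.575, 0.497→0.495, 0.449→0.447 |
| 0.5 | 1.02, 1.02, 1.01 | 0.549→0.558, 0.487→0.494, 0.411→0.421 |
| 1.0 | 1.12, 1.09, 1.07 | 0.463→0.508, 0.411→0.450, 0.395→0.409 |
| 1.5 | 1.28, 1.21, 1.11 | 0.366→0.442, 0.359→0.412, 0.355→0.387 |

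The power column is for the Wald test of the arm term. Slope 1.5 is a stress case beyond the range used for the conclusion.

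**Check 3: what the indicator already achieves.** The risk-difference variance with no baseline adjustment was 1.13–1.22 times that of the planned model. The planned term thus already delivers a useful gain.

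**Check 4: the odds-ratio scale.** At slope 1.0, the standard error of the log odds ratio rises with the extra term: 0.43 to 0.47, 0.47 to 0.51 and 0.51 to 0.54 at 40%, 60% and 75% suppressed. The estimate rises too. At 40% suppressed, mean estimate over median standard error goes from 0.81/0.431 = 1.88 to 0.95/0.473 = 2.01, and (2.01/1.88)² = 1.14. The gain is therefore in the test and in the risk difference, not in a narrower interval for the odds ratio.

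**The case against.** The strongest reply is that the planned adjustment is valid and the alternative is no better on the scale the plan reports. Most of the reply's components stand.

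- **Standard error.** It rises for the log odds ratio, as Check 4 shows. In a further run at odds ratio 2.5, the extended model's root-mean-square error around 0.916 was larger in all six settings (for example 0.499 against 0.451 at slope 1.2 with 30% suppressed). That comparison favours the planned model because its odds ratio is pulled toward 1, which also shrinks its spread. It does not show a more efficient analysis.
- **Bias.** A reader might infer that the planned odds ratio is biased: at slope 1.2 the planned model's mean log odds ratio was 0.77–0.82 against 0.92. The documents do not support this. The 0.92 is conditional on the numeric load, and a model without that term targets a different odds ratio (non-collapsibility). In Check 2 at slope 1.0 the extended model itself averaged 0.95–0.98 against 0.9, a small-sample overshoot.
- **Chance imbalance.** A reader might treat it as a separate systematic error. Under randomization it adds variance only.
- **Quality of the predictor.** The values come from medical records with no stated window around baseline, and some eligible men have had fewer than 2 visits in 12 months. Dated values would weaken the slope, and with it the gain.
- **Status of the analysis.** It is exploratory, the plan expects insufficient power for multivariate models, and keeping parameters few is defensible.
- **Other provisions.** The log viral load change analysis uses the number, but for a different outcome. Further covariates may be chosen with the help of Fig. 1, which is not shown in the text available, so numeric load cannot be proved excluded. Still, the sentence on this model fixes the dichotomized form, and selection by bivariate baseline analyses cannot show how baseline load predicts suppression at 6 months.

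**Conclusion.** The point holds as a minor, optional improvement. The suppression model ignores recorded information among men unsuppressed at baseline. The cost is from nil to about 15% in information for slopes from 0 to 1.2 log-odds per log10, or at most about 6 points of power. In the stress case of slope 1.5 the planned model's risk-difference variance was 11–28% higher.

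These sizes rest on an assumed slope, suppression rate and spread of viral loads, none of which the documents give, and on timely baseline values. No stated figure in the plan is wrong, and no conclusion of a feasibility pilot depends on this choice. The case for changing it is the asymmetry: about 1% lost if the value carries no prognostic information, against a modest gain if it does, in analyses meant to help plan a full trial.

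**What to change.** In section 5, in the sentence on the 6-month suppression model, replace the single dichotomized baseline term with two: the suppressed/not suppressed indicator, and log10 baseline viral load for men at or above 200 copies/mL, set to zero otherwise. Values below an assay limit then cause no difficulty, because the indicator covers those men.

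State that the covariate-standardized risk difference will be reported beside the odds ratio, since that is the scale on which the precision gain appears.

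The cost is one or two sentences, one extra parameter and no new data, with about 1% efficiency lost if the value is not prognostic. The log odds ratio will have a larger standard error and will refer to a more conditional effect, which the report should say.

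### Log viral load is analysed as change from baseline with no stated adjustment for the baseline value, which gives up precision in an exploratory contrast

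*Combined protocol and SAP*

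**What the plan says.** Section 5 (Statistical Analysis) of the combined protocol and SAP treats viral load in two ways.

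- Binary: "We will conduct logistic regressions predicting viral load (dichotomized as suppressed vs. not suppressed) at 6-months post-baseline with dichotomized baseline viral load". Baseline is in this model.
- Continuous: the model comes from the general statement "We will use similar repeated-measures linear models to examine intervention effects on the other secondary outcomes", which continues "as well as on linear adherence (percentage of prescribed doses taken) and log viral load change from baseline". No baseline term is named.

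The template for those linear models is the one for coping, fitted "with data collected at baseline and 4- and 6-month follow-up that compares differences between intervention and control means over time". There the baseline value enters as one of the responses. Nothing says that the two arms share a common baseline mean.

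A later sentence governs covariates in general: "We will select covariates from variables that are hypothesized on the basis of theory and previous research to predict outcome variables". It adds that the hypotheses must find support in bivariate analyses at baseline. Baseline log viral load is neither named nor excluded.

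On the data source, Section 4 (Procedures) says: "We will obtain HIPAA consent to extract the last two viral load values from medical records". On size, Section 3 says: "We will conduct 4 intervention groups and 4 wait-list control groups of 15 participants each (n=120".

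**The concern.** A change score fixes the slope of follow-up on baseline at 1. If the true slope differs, part of the baseline value stays in the response as noise. Any chance difference between the arms at baseline then carries through to the estimate. Adjusting for baseline lets the data set the slope and removes that part.

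The eligibility rule in Section 4 admits men not on antiretroviral treatment alongside men on treatment who missed as little as one dose in a month. A wide spread of baseline values is therefore plausible, and the choice of slope could matter. What is at stake is the precision of one contrast meant to help plan a later full trial. The plan also treats baseline differently for the binary and continuous forms of the same measurement and gives no reason.

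**Working it through.** **The plan's own figure.** (4 + 4) × 15 = 120, and 4 × 15 = 60 per arm, as Section 3 states. There is no power, alpha, effect size or variance figure to reproduce.

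**Inputs not in the documents (assumptions).** The correlation r between baseline and follow-up log viral load, and the ratio k = follow-up SD / baseline SD. I take r from 0 to 0.9, and k = 0.75, 1 and 1.25.

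**Does the repeated-measures form already solve it?** With two time points, complete data and no constraint on the baseline means, the group-by-time contrast is (follow-up difference) − (baseline difference). That is the difference in mean change, so the label alone recovers nothing.

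**Variance with equal SDs.** In units of the common variance:

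- change score: 2(1−r)
- adjusted for baseline: 1−r²
- proportional reduction: 1 − (1−r²)/[2(1−r)] = (1−r)/2

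| r | Change | Adjusted | Variance reduction | SE reduction |
|---|---|---|---|---|
| 0 | 2.00 | 1.00 | 50% | 29% |
| 0.3 | 1.40 | 0.91 | 35% | 19% |
| 0.5 | 1.00 | 0.75 | 25% | 13% |
| 0.7 | 0.60 | 0.51 | 15% | 8% |
| 0.9 | 0.20 | 0.19 | 5% | 3% |

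The SE reduction is 1 − √(adjusted/change). A simulation with 60 per arm and 20,000 runs at each r gave variance reductions of 34.4%, 25.5% and 15.3% at r = 0.3, 0.5 and 0.7.

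**Variance with unequal SDs.** The reduction is 1 − k²(1−r²)/(1+k²−2rk), which simplifies to (1−rk)²/(1+k²−2rk).

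| k | r = 0.3 | r = 0.5 | r = 0.7 |
|---|---|---|---|
| 0.75 | 54% | 48% | 44% |
| 1 | 35% | 25% | 15% |
| 1.25 | 22% | 11% | 2% |

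The numerator is a square, so in large samples the reduction is never negative. It is zero only when the slope rk equals 1, for example k = 1.25 with r = 0.8.

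**Where the loss comes from.** With equal SDs, 2(1−r) = (1−r²) + (1−r)². The last term is the contribution of chance baseline imbalance: 1.40 = 0.91 + 0.49, 1.00 = 0.75 + 0.25, and 0.60 = 0.51 + 0.09.

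For a baseline difference d, the change-score estimate shifts by −(1−r)d. The simulated slopes were −0.70, −0.51 and −0.31, against about 0 after adjustment. With 60 per arm, the SD of d is √(2/60) = 0.18 baseline SDs. A shift of typical size is therefore 0.13, 0.09 or 0.05 SD at r = 0.3, 0.5 and 0.7. Relative to the change-score standard error this is √[(1−r)/2] = 0.59, 0.50 or 0.39, and that standard error already contains it.

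**The case against.** The case for leaving the text alone has four parts.

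1. **The wording may name the effect, not the response.** The phrase sits in a list of outcomes under mixed models that take baseline in as a response. The covariate rule might also admit baseline log viral load. It is fair to say that adjustment is unspecified rather than ruled out. But an unconstrained mixed model gives the change-score contrast anyway. The covariate rule asks for support in analyses at baseline, where the change does not yet exist, so it gives no sure route to this term.
2. **The size is unknown.** This stands. No r or SD is given, and with k = 1.25 and r = 0.7 the gain is only 2%. The direction does not depend on these inputs.
3. **The estimate is valid as it is.** This stands too. The change score is unbiased over randomization, and its standard error already reflects chance imbalance. The complaint is about precision only.
4. **The analysis is exploratory.** Section 5 says that the sample does not justify formal outcome tests. Section 2 names suppression as the viral load aim, and that model already includes baseline. This limits the priority, but it is no reason to keep a less precise contrast when the remedy is free.

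**Conclusion.** The concern holds as a minor point of specification. Section 5 analyses log viral load as change from baseline and states no baseline adjustment, unlike its own suppression model. The resulting contrast is valid but generally less precise than the same data allow.

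With equal SDs the gain from adjustment is (1−r)/2, so 15% to 35% of the variance for r = 0.7 to 0.3 and 5% to 50% for r = 0.9 to 0. Unequal SDs move it to between 2% and 54% over r = 0.3 to 0.7 and k = 1.25 to 0.75. Both r and k are assumptions. Group clustering, values below the assay limit and dropout are left out because the documents give no figures for them.

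A reader might infer more than this, and the documents do not support it:

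- That a loss of 15% to 35% is established for this trial. That range needs equal SDs and r between 0.3 and 0.7, and the plan gives neither.
- That lost precision and exposure to baseline imbalance are two harms. They are one quantity, as the decomposition shows.
- That the estimate is biased. It is not, over randomization.
- That the two extracted values are the baseline and 6-month values and are already in hand. Section 4 describes consent to be obtained for the last two values in the record, and gives no dates for them.

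**What to change.** Add one sentence to Section 5 in either of these forms:

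- 6-month log viral load will be regressed on arm, with baseline log viral load as a pre-specified covariate. Using the change as the response is equivalent once baseline is in the model: if y − b = α + βg + γb, then y = α + βg + (γ+1)b, with the same arm effect β.
- Log viral load will be analysed in the planned mixed model, with the baseline mean constrained to be equal across arms.

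The cost is one degree of freedom and the sentence itself. No new data are needed beyond what the plan already implies, since both the change score and the suppression model require a baseline and a 6-month value.
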